#### 3. Trial method

#### 3.1 Trial design

The trial was a placebo-controlled randomized double-blind comparative study (Phase I/II clinical trial) of four dose parallel groups: placebo, low-dose (0.5 g/administration/day), intermediate-dose (1.0 g/administration/day), and high-dose (1.5 g/administration/day).

- Dosage and dose: The subject will take three sticks of trial drug once daily before breakfast. Consecutive administration for five days constitutes one course, with a total of four courses administered from the first administration (Day 1 to Day 5), Day 8 to Day 12, Day 22 to Day 26, and Day 50 to Day 54. However, the dose on Day 1 will be administered between meals in the hospital.
- Trial period: 16 weeks. Primary evaluation at 16 weeks after first dose.
- Follow-up period: eight weeks. Pathological evaluation (biopsy) was performed 16 weeks after the first dose to avoid missing patients who had progressed to invasive cancer; if the lesion was CIN3 or lower, the patients were again evaluated pathologically 24 weeks after the first dose. If a patient was diagnosed clinically as CIN3 or more at week 16, she received standard therapy.

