## Table 1 Observation / survey and test items during the trial (follow-up) period

1

Item	Eligibi	ility nation period	Trial p	Trial period									Follow-up period		
	Initia 1 visit	Administrati on start day Day 1	(Wee k 1)	(Wee k 2)	(Wee k 3)	(Wee k 4)	(Wee k 5)	(Wee k 6–7)	(Wee k 8)	(Wee k 9)	(Wee k 10–15 )	(Wee k 16)	(Wee k 17–23 )	(Wee k 24)	At discontinuati on
Visit															
Permitted range of visit															
Prescription of trial drug															
Administratio n of trial drug															
Confirmation of drug administration status															
Consent acquisition															

Confirmation of selection / exclusion criteria								
Case registration								
HPV genotype test (for eligibility confirmation)								
HPV genotype test (central test)								
Histology (central pathological judgment)								
Histology (implementin g medical facility judgment)								
Histology								

Colposcopy								
Laboratory test								
Pregnancy reaction (serum hCG)								
HIV test								
HPV16E7 protein expression level								
E7 protein expression (cervical cells)								
HPVE7-specif ic immune response								
Subjective symptoms h / objective findings								

Concomitant drugs / therapies								
Confirmation of medical history and complications								
Confirmation of adverse events i								

 $\circ$ : Item that is implemented before the start of administration or confirms the test results;  $\bullet$ : Item that is implemented after the start of administration;  $\triangle$ : Item that is implemented in case of suspected invasive cancer;  $\bigcirc$ : Item that is implemented only on cases judged to be applicable in the follow-up survey at 16 weeks after administration

a: Implement test for selection/exclusion criteria confirmation after consent

b: Confirm eligibility based on applicable data in case there is data within 90 days prior to consent (data at another hospital, in-hospital data not required). Implement the test after consent in case there is no applicable data.

c: Implement test using E7 protein expression specimen collected on the same day

d: Confirm no problem with the test results (no possibility of pregnancy) before prescription of the trial drug. Administration of the trial drug shall start within 10 days from the day when the applicable laboratory test was conducted.

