#### 4.1.2 Secondary endpoints

1) Regression rate at 24 weeks after the first dose

2) HPV E7-specific immune response: before trial drug administration, 16 and 24 weeks after the first dose.

The presence or absence of HPV E7-specific immune response at 16 weeks after the first dose and at 24 weeks after the first dose will be used as an endpoint. Separately, the presence or absence of HPV E7-specific immune response prior to the first dose will be used as a stratification factor for stratified analysis.

3) Change in HPV 16 E7 molecule protein expression level: at 16 and 24 weeks after the first dose.

HPV 16 E7 molecule protein expression level will involve measurements of the expression level (copy/ng) by relative quantification before first administration of the trial drug, and at 16 and 24 weeks after the first dose. The expression level by absolute quantification will also be measured only before the first administration of the trial drug. The magnitude and rate of change of the expression level (relative quantification value) from before first administration to 16 and 24 weeks after the first dose will be the endpoint. Separately, the expression level (absolute quantitative value) before the first dose is used as a stratification factor for stratification analysis. For this stratification factor, two categories of "below median" and "above median" and three categories of "below first tertile," "above first tertile, below second tertile," and "above second tertile" will be used.

4) Improvement in cytology\* of HSIL/CIN 2-3 lesions: at 16 and at 24 weeks after the first dose. Changes in lesions in cytology are judged by any of the following in subjects diagnosed with HSIL at the time of registration.

PR: Change to LSIL, ASC-US, or NILM

SD: No change from HSIL

PD: Change to SCC

NE: Change to AGC or ASC-H

\* Cytology: Cytological tests of the cervix will be conducted before trial drug administration, nine weeks after the first dose, 16 and 24 weeks after the first dose.

5) Percentages of "CR," "PR," "SD," and "PD" in the pathological improvement indicators of cervical intraepithelial neoplasia lesions: at 16 and 24 weeks after the first dose.

6) Presence or absence of changes in the HPV16: at 16 and 24 weeks after the first dose.HPV genotype test: conducted before trial drug administration, 16 and 24 weeks after the first dose (applicable cases only) to measure the HPV genotype.

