6.4.4 Range of data adoption for evaluation periods

Table 2 shows the trial protocol-stipulated evaluation periods and the corresponding time intervals of the efficacy endpoints of histology, cytology, presence or absence of an HPV E7-specific immune response, and HPV genotype changes, as well as the safety endpoints of laboratory tests. In practice, the tests may be conducted at a time point outside the defined time interval. Therefore, the range of data adoption is defined in the rightmost column of Table 2, and the following two points are set as the policy for setting the range of data adoption in such cases:

1) For the four visits at weeks 5, 9, 16, and 24, for which laboratory test measurements are planned, there should be no overlap in the two ranges of data adoption that correspond to two adjacent visits, and no gaps in time.

2) For weeks 5, 9, and 16, the upper limit of the range of data adoption should be one week after the last day of the permissible range of visits (e.g., for week 5, the range should be until day 49, which is one week after day 42, i.e., the last day of that week).

The data obtained within the range of data adoption should be adopted as the data of the corresponding visit. For example, if histology was conducted within the range of day 85–day 133, then the results will be adopted as data at the end of the trial (16 weeks after first administration).

Evolution	Time interval	Test item		Danga	f data		
period	(according to	Histology	Cytology	HPV*	Laboratory	adoption	i data
_	clinical trial				test		

Table 2. Trial protocol-stipulated evaluation period and range of data adoption

	protocol)					
First visit		0	0			~ Day1
Administration	Day 1			0	0	~ Day1
start day						
Week 1	Day 2–7					
Week 2	Day 8–14					
Week 3	Day 15–21					
Week 4	Day 22–28					
Week 5	Day 29–42**				•	~ Day 2–49
Week 6–7	Day 36–49					
Week 8	Day 50–56					
Week 9	Day 57–77**		•		•	~ Day 50–84
Week 10–15	Day 64–105					
Week 16	Day	•	•	•	•	~ Day 85–133
	106-126**					
Week 17–23	Day 113–161					
Week 24	Day	0	0	0	0	~ Day 134
	162–182**					
At		•	•	•	•	
discontinuation						

\* HPV: HPVE7-specific immune response, HPV genotype

\*\* : Permissible range of visit

 $\circ$ : Implemented before start of administration;  $\bullet$ : Implemented after start of administration;  $\odot$ : Implemented only for cases subject to follow-up survey

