#### 4) Effect of HSIL/CIN 2-3 lesions on cytology

For FAS and PPS, for subjects diagnosed with HSIL at registration, the percentages of "PR," "SD," "PD," and "No judgment" are calculated for each group at weeks 16 and 24. The denominator of the percentage (%) of each judgment is the number of cases in the analysis set. Furthermore, for the FAS, the same tabulation is conducted by stratification using stratification factors.

5) Percentages of "CR," "PR," "SD," and "PD" in the histopathological evaluation indicators of cervical intraepithelial neoplasia

For FAS and PPS, the percentages of "CR," "PR," "SD," and "PD," and "No judgment" are calculated for each group at weeks 16 and 24. The denominator of the percentage (%) of each judgment is the number of cases in the analysis set. Furthermore, for the CR rate, Fisher's exact test is used for pairwise comparisons between each dose group and the placebo group. Additionally, the dose-response relationship is investigated with the same contrasts as in Section 7.3.1.1). For FAS, the same tabulation is conducted by stratification using the stratification factors.

6) Evaluation of changes in the HPV genotype

For FAS and PPS, the percentages of the number of cases for judgment categories ("negative," "positive, but not including type 16," "HPV16 only," "HPV16+other types," and "no judgment") are calculated for each group at weeks 16 and 24, with the number of cases for each judgment of "HPV16 only" and "HPV16+other types" before trial drug administration. Separately, the number and percentage of cases is calculated for the category of "clearance of HPV16" by merging "negative" and "positive, but not including HPV16." Furthermore, for FAS, the same tabulation is conducted by stratification using the stratification factors.

7) Disease control rate

For FAS and PPS, the percentage of subjects with histology of CIN3 at

registration improving to CIN2 or lower at weeks 16 and 24 is calculated for each group, and their 95% confidence intervals (Clopper–Pearson method) are calculated. Additionally, Fisher's exact test is used for pairwise comparisons between each dose group and the placebo group. Furthermore, for FAS, the same tabulation is conducted by stratification using the stratification factors.

Definition:

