• For subjects diagnosed with HSIL at registration, the judgment categories for the effect of HSIL/CIN 2-3 in cytology are set as "PR," "SD," "PD," and "no judgment." Here, "no judgment" includes "NE" and missing judgment results because of tests not being conducted, etc.

• The judgment categories for pathological improvement indicators of cervical intraepithelial neoplasia are set as "CR," "PR," "SD," "PD," and "no judgment." Here, "no judgment" includes "NE" and missing judgment results because of tests not being conducted, etc.

• The judgment categories for HPV genotype are set as "negative," "positive, but not including HPV16," "HPV16 only," "HPV16+other types," and "no judgment." Here, "no judgment" includes missing judgment results because of tests not being conducted, etc.

• If either of the two time points is "NE" or the judgment result is missing, the judgment result at the other time point is set as the best effect. When a judgment result is not obtained at either of the two time points, the best effect is set as "no judgment."

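### Week-24 cytology and HPV16 percentages count women untested by design, so they are capped by retention in follow-up and can move with exit rather than with any true change

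*SAP*

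**What the plan says.** **Who is tested.** At week 16, cytology and HPV genotype are planned for all women. At week 24 the Table 2 legend (SAP 6.4.4) marks tests as "Implemented only for cases subject to follow-up survey", and the Table 1 legend agrees: "Item that is implemented only on cases judged to be applicable in the follow-up survey at 16 weeks after administration". Section 4.1.2 item 6) repeats the limit for HPV: "16 and 24 weeks after the first dose (applicable cases only) to measure the HPV genotype". The cytology footnote in 4.1.2 omits it ("Cytological tests of the cervix will be conducted before trial drug administration, nine weeks after the first dose, 16 and 24 weeks after the first"), so for cytology the restriction comes from the two tables.

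**Who leaves.** Section 3.1 says "If a patient was diagnosed clinically as CIN3 or more at week 16, she received standard therapy". Section 1.2 describes exit as limited to CIN3 that requires treatment, or invasive cancer. Under either text, exit follows from the week-16 diagnosis.

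**How untested women are counted.** In the 7.3.2 Definition for HPV genotype: "Here, 'no judgment' includes missing judgment results because of tests not being conducted, etc". The cytology definition is parallel, but adds NE to the same category. Item 4) on cytology states "The denominator of the percentage (%) of each judgment is the number of cases in the analysis set". Item 6) tabulates genotype within baseline HPV16 categories, with *no judgment* as one of the outcomes. It then forms a clearance category without giving that percentage its own denominator.

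**Missing data.** Section 6.5 does not impute in general. Its two week-24 rules (normal stays normal, CIN3 stays CIN3) concern histology. Cytology and HPV have no counterpart.

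**The concern.** A woman who has cleared HPV16, or improved in cytology, at week 16 and then leaves follow-up because of her histology is a success in the week-16 table. At week 24 she sits in *no judgment*: still in the denominator, but unable to count as a success. The week-24 percentage then mixes two things, the cytological or virological result and the share of women whose week-16 histology kept them under test.

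That share is tied to the primary outcome. If a dose improves week-16 histology, more of its women are tested at week 24, and its clearance and PR percentages rise relative to placebo even if it does nothing to either. Both endpoints are named secondary endpoints at both visits and are tabulated by dose group in a trial meant to determine a recommended dose. A reader comparing arms at week 24, or week 24 with week 16, could take an effect of exit for loss of response or for a dose effect.

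**Working it through.** The SAP gives no retention, clearance or cytological response rate, so there is no plan figure to reproduce. The group size of 41 is from SAP 3.3. All rates below are assumptions.

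**Notation.** For one arm, *r* is the share retained in follow-up, *s* the success rate among those retained, and *q* the success rate among leavers. Each woman's status is assumed unchanged from week 16 to week 24. On the full denominator:

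- Week 16 = r·s + (1 − r)·q
- Week 24 as planned = r·s
- Fall with no true change = (1 − r)·q
- Ceiling on week 24 = r
- Gap between arms added by exit, with the same *q* in both = (r_active − r_placebo)·q

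**Ceiling with 41 women.** If 12 leave, it is 29/41 = 70.7%. If 25 leave, it is 16/41 = 39.0%.

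**Fall and arm gap for HPV16 clearance** (placebo / active, %):

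| Retention | s | q | Week 16 | Week 24 as planned | Gap added by exit (points) |
|---|---|---|---|---|---|
| 40 / 65 | 25 | 25 | 25.0 / 25.0 | 10.0 / 16.25 | 6.25 |
| 40 / 65 | 35 | 10 | 20.0 / 26.25 | 14.0 / 22.75 | 2.5 |
| 40 / 65 | 35 | 0 | 14.0 / 22.75 | 14.0 / 22.75 | 0 |
| 80 / 90 | 25 | 25 | 25.0 / 25.0 | 20.0 / 22.5 | 2.5 |
| 65 / 65 | 25 | 25 | 25.0 / 25.0 | 16.25 / 16.25 | 0 |

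Second row in full. Placebo at week 16 is 0.40 × 0.35 + 0.60 × 0.10 = 0.20, and at week 24 it is 0.40 × 0.35 = 0.14. Active at week 16 is 0.65 × 0.35 + 0.35 × 0.10 = 0.2625, and at week 24 it is 0.65 × 0.35 = 0.2275. The gap grows from 6.25 to 8.75 points, so exit adds 2.5 points, or 0.025 × 41 ≈ 1 woman per arm.

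The last row shows that with equal exit the arm artefact vanishes, but both arms still fall by 8.75 points.

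**Cytology.** The same formulas apply. Item 4) covers women with HSIL cytology at registration. Whether its denominator is read as that subgroup or literally as the whole analysis set, untested women remain in it.

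**How large exit could be.** SAP 3.3 places 10 women with CIN2 in each group of 41, so 31 enter with CIN3. Substantial exit is therefore possible, but the SAP does not fix the share. Section 3.1 sends women with CIN3 or more to standard therapy, yet also says that lesions of CIN3 or lower are evaluated again at week 24. Section 1.2 excludes only CIN3 requiring treatment and invasive cancer. A test at discontinuation from day 134 onward could be adopted as week-24 data (6.4.4), which may recover a few women.

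**The case against.** **The tables are descriptive and the shortfall is shown.** Items 4) and 6) plan no test and no confidence interval, *no judgment* is tabulated per group and visit, 7.1.1 reports completion of follow-up per group, and individual efficacy data are listed. This stands and limits the severity. Women who leave are not shown as HPV16-positive. But for cytology the *no judgment* row pools women untested by design, missed tests and NE, and NE includes actual AGC or ASC-H results. The reader cannot rescale to tested women from that row.

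**Counting leavers as not improved may be a deliberate composite.** It is a defensible choice, consistent with the primary regression rate, which also divides by all FAS cases, and it causes no fall if no leaver had succeeded (*q* = 0). The SAP does not say that it makes this choice, and it uses a different rule for histology.

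**Stronger readings that do not hold.** A reader might infer that the plan explicitly divides HPV16 clearance by the full analysis set. It does not; that denominator is unstated. A reader might also take arm gaps of 6 points for clearance, or 12.5 points for cytological PR (50% × 40% versus 50% × 65%), as the expected bias. Those figures need success to be unrelated to leaving, whereas leaving is decided by CIN3 or worse at week 16. If leavers succeed less often than stayers, the artefact shrinks with *q*. Finally, a reader might want week-16 HPV and cytology carried forward by analogy with 6.5. The analogy fails: for women leaving with CIN3, 6.5 carries forward an unfavourable result, whereas this would count favourable week-16 results as week-24 successes in women who may since have had standard therapy.

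**Conclusion.** The point holds as a defect of tabulation and labelling, of moderate weight. As written, week-24 cytological PR is capped at the share of women in its denominator who are still in follow-up. HPV16 clearance is capped likewise if its denominator is the baseline category. Both can fall from week 16 with no true change, by (1 − r)·q.

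The distortion between arms is conditional. It needs unequal exit and some success among leavers, and equals the product of the two. At an assumed 40% versus 65% retention it is 2.5 points with 10% clearance among leavers and 6.25 points with 25% clearance unrelated to leaving. It is smaller with higher or more equal retention, and zero if exit is equal with the same *q*, or if no leaver succeeds. The documents do not support a claim that the arm comparison is biased by a known amount. The actual size cannot be fixed while Sections 1.2 and 3.1 disagree on who leaves.

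**What to change.** In SAP 7.3.2 items 4) and 6), for week 24:

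1. Show women outside follow-up by design in their own row, separate from NE and from missed tests.
2. State the denominator for HPV16 clearance. For both endpoints, report the number tested per arm and the percentage among tested women beside the full-denominator percentage.
3. Add a paired table of week-16 and week-24 results in women tested at both visits, to describe durability.
4. State that the between-arm description of HPV16 clearance and cytology rests mainly on week 16, where testing is planned for all women.

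Do not carry forward week-16 HPV or cytology results. Separately, reconcile Sections 1.2 and 3.1 on who leaves follow-up at week 16, and align the cytology footnote in 4.1.2 with the limit in Tables 1 and 2.

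Cost: SAP wording, a few extra descriptive rows and one table per endpoint. The tested-only percentage describes a selected group and should be labelled so; it complements the full-denominator figure and does not replace it.

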#### 7.3.3. Exploratory analysis

1) Investigation of the distribution of the E7 protein expression level (absolute quantification value) before first administration

Target FAS

population:

Analysis Calculate summary statistics (number of cases, mean, standard deviation, content: minimum, median, maximum, first quartile, third quartile) of the E7 protein expression level (absolute quantification value) and display them in a box plot for each diagnosis (CIN2, CIN3) and the overall diagnosis.

2) Investigation of the relationship between the E7 protein expression level (absolute quantification value) before first administration and the improvement effect of IGMKK16E7

Target FAS

population:

Analysis Explore whether the E7 protein expression level (absolute quantification value)

content: before the first dose can be a predictor of the therapeutic effect of IGMKK16E7. Here, a predictor of the therapeutic effect is a factor for which a higher therapeutic effect of IGMKK16E7 can be expected according to its value. The regression rate at weeks 16, which is the primary endpoint, is used as the therapeutic effect. The specific analysis procedure is described below.

1. Cases when the E7 protein expression level before first administration are divided into two categories (see definition section):

1-1) The following analysis is conducted for each of the three cases related to the presence or absence of IGMKK16E7 administration (see definition section). 1-2) Set a value, C, for all possible classifications of E7 protein expression level before first administration. For each C, the number of cases and the response rate are calculated for the presence or absence of IGMKK16E7 administration for each of the categories "less than C" and "C or greater." However, when the number of cases for either "administration present" or "administration absent" is less than two, the analysis using the applicable classification value C will not be conducted.

1-3) For each C, conduct a logistic regression analysis where the presence or absence of response is set as the response variable; and the presence or absence of IGMKK16E7 administration, E7 protein expression level before first administration, and interaction between the presence or absence of IGMKK16E7 administration and E7 protein expression level before first administration (henceforth, referred to as "interaction") are set as the explanatory variables. Then, record the p-value of the interaction. Additionally, create a plot of the p-value of the interaction for each case.

1-4) Referencing the p-value plot of the above-mentioned interaction, output the analysis result under each of the classification values among all the possible classification C values where the p-value of the interaction is at a minimum (or 2–3 that are close to the minimum). Specifically, output the estimated value of the regression coefficient of the logistic regression as well as the odds ratio of the IGMKK16E7 response with respect to that of the placebo for each category of "less than C" and "C or greater" of the E7 protein expression level before the first administration. Additionally, create a plot of the estimated value of the response rates for each of the IGMKK16E7 and placebo for each category of "less than C" and "C or greater" of the E7 protein expression level before the first administration, and their two-sided 95% confidence interval. Use the Clopper–Pearson method to calculate the 95% confidence interval.

2. Cases where the E7 protein expression level before first administration is classified into three categories:

2-1) Conduct the following analyses in each of the three cases related to the presence or absence of IGMKK16E7 administration.

2-2) Set all possible classification value pairs C1 and C2 (>C1) of the E7 protein expression level before first administration. For each pair of C1 and C2, calculate the number of cases and the response rate of the presence or absence of IGMKK16E7 administration for each category of "less than C1," "C1 or greater and less than C2," and "C2 or greater." However, when the number of cases for either "administration present" or "administration absent" is less than two, the analysis using the applicable classification value pair C1 and C2 will not be conducted.

2-3) For each pair C1 and C2, conduct a logistic regression analysis where the presence or absence of a response is set as the response variable; and the presence or absence of IGMKK16E7 administration, E7 protein expression level before first administration, and interaction between the presence or absence of IGMKK16E7 administration and E7 protein expression level before first administration (henceforth, referred to as "interaction") are set as the explanatory variables. At that time, the E7 protein expression level before first administration is treated as a continuous explanatory variable with three levels of ordinal category values. For each case, record the p-value of the interaction. Additionally, create a plot of the p-value of the interaction for each case.

2-4) Referencing the p-value plot of the above-mentioned interaction, output the analysis result under each of the classification value pairs among all the possible classification value pairs C1 and C2, where the p-value of the interaction is at a minimum (or 2–3 that are close to the minimum). Specifically, plot the estimated value of the regression coefficient of the logistic regression as well as the estimated value of the response rate for each category of "less than C1," "C1 or greater and less than C2," and "C2 or greater," of the E7 protein expression level before the first administration. Calculate and plot their two-sided 95% confidence intervals using the Clopper–Pearson method.

Definition: Response variable: set as the presence or absence of response at week 16. This is the primary endpoint of this trial.

Explanatory variables: E7 protein expression level before first administration and presence or absence of IGMKK16E7 administration (total = two variables); multiple cases are investigated for each.

• E7 protein expression level before first administration. The following two cases are investigated:

Case	Category
Two categories	"Less than C," "C or higher"
Three categories	"Less than C1," "C1 or higher and less than C2,"
	"C2 or higher"

C (or C1 and C2) is the scaled classification value of the E7 protein expression level. Order statistics of the E7 protein expression level are used to set all possible values of the classification value C (or C1 and C2) in a sequential manner. At that time, classification values in either of the two categories of "less than C" or "C or higher" (or three categories of "less than C1," "C1 or higher and less than C2," or "C2 or higher"), where the number of cases for either category of "administration present" or "administration absence" of the IGMKK16E7 administration below is less than two, are excluded from the investigation.

• Presence or absence of IGMKK16E7 administration. The following three cases are investigated.

Case	IGMKK16E7 administration		Content
	Administration	Administratio	
	present	n absent	
1	High-dose group	Placebo	IGMKK16E7 vs. placebo
	+	group	
	intermediate-dos		
	e group +		
	low-dose group		
2	High-dose group	Placebo	High and intermediate dose
	+	group	of IGMKK16E7 vs.
	intermediate-dos		placebo
	e group		
3	High-dose group	Placebo	High dose of IGMKK16E7
		group	vs. placebo

3) Investigation of the relationship between changes in the E7 protein expression level (relative quantification value) after administration and pathological judgment

Target FAS

population:

Analysis For each of the three IGMKK16E7 dose groups of the IGMKK16E7 content: administration group (high-dose group + intermediate-dose group + low-dose group) and the placebo group, summary statistics are calculated for the magnitude and rate of change in the E7 protein expression level (relative quantification value) after administration for each category of the pathological judgment results after administration.

> • Categories of pathological judgment results: "CR," "PR," "SD," "PD," "NE," "response (CR or PR)," and "non-response (SD or PD)"

• Evaluation time points: 16 and 24 weeks after the first dose

4) Investigation of the relationship between the presence or absence of an HPV E7-specific immune response before first administration and the improvement effect of IGMKK16E7

Target FAS

population:

Analysis Conduct a logistic regression analysis where the presence or absence of a content: response is set as the response variable; the presence or absence of IGMKK16E7 administration, presence or absence of an HPV E7-specific immune response before first administration, and the interaction between the presence or absence of IGMKK16E7 administration and the presence or absence or

Based on this result, output the estimated value of the regression coefficient of the logistic regression as well as the odds ratio of the IGMKK response with respect to that of the placebo for each category of "no response" and "response" of the HPV E7-specific immune response before first administration. Furthermore, create a plot of the estimated value of the response rates for each of the IGMKK and placebo for each category of "no response" and "response" of the HPV E7-specific immune response before the first administration. Calculate and plot their two-sided 95% confidence interval using the Clopper–Pearson method.

Definition: Response variable: set as the presence or absence of a response at 16 weeks

after the first dose. Explanatory variables: presence or absence of an HPV E7-specific immune response and presence or absence of IGMKK16E7 administration (total = two variables). The same three cases are investigated as in point 2) mentioned above for the presence or absence of IGMKK16E7 administration.

5) Investigation of the relationship between the presence or absence of an HPV E7-specific immune response after administration and pathological judgment

Target FAS

population:

Analysis For each of the three IGMKK16E7 dose groups of the IGMKK16E7 content: administration group (high-dose group + intermediate-dose group + low-dose group) and the placebo group, a contingency table is created between the pathological judgment result after administration and the presence or absence of an HPV E7-specific immune response.

> • Categories of pathological judgment results: "CR," "PR," "SD," "PD," "NE," "response (CR or PR)," and "non-response (SD or PD)"

• Evaluation time points: 16 and 24 weeks after the first dose

6) Investigation of the relationship between the HPV E7-specific immune response SFC value after administration and pathological judgment

Target FAS

population:

Analysis For each of the three IGMKK16E7 dose groups of the IGMKK16E7 content: administration group (high-dose group + intermediate-dose group + low-dose group) and the placebo group, summary statistics are calculated for the HPV E7-specific immune response SFC value after administration for each category of the pathological judgment results after administration.

• Categories of pathological judgment results: "CR," "PR," "SD," "PD," "NE,"

"response (CR or PR)," and "non-response (SD or PD)"

• Evaluation time points: 16 and 24 weeks after the first dose

7) Investigation of the relationship between the log-transformed HPV E7-specific immune response SFC value after administration and pathological judgment

Target FAS

population:

Analysis For each of the three IGMKK16E7 dose groups of the IGMKK16E7 content: administration group (high-dose group + intermediate-dose group + low-dose group) and the placebo group, summary statistics (number of cases, mean, standard deviation, minimum, median, maximum, first quartile, third quartile) are calculated for the magnitude of change of the log-transformed SFC value (geometric mean value ratio) and log-transformed SFC value after administration for each category of the pathological judgment result after administration. Note that the value 0.0 is read as 0.001 in log-transformation.

• Categories of pathological judgment results: CR," "PR," "SD," "PD," and "NE"

• Evaluation time points: 16 and 24 weeks after the first dose

• In addition to the above, the best change in log-transformed SFC value (bigger value between 16 and 24 weeks after first administration)

Additionally, all the above-mentioned results are displayed in a box plot.

